### *Aortic Delivery System*

The working length of the aortic delivery system is  $57 \pm 2\text{cm}$ . The aortic delivery system is constructed of four concentric single lumen shafts (an outer polymer graft cover with a hydrophilic coating, a heat shrink covered laser cut stainless steel spindle-tube shaft, a polymer middle member shaft, and a nitinol guidewire tube lumen inner member).

[REDACTED]. The aortic delivery system is used to deliver the bifurcated, AUI, and aortic extension stent graft components. Figure 2 provides a

pictorial reference of the Endurant Evo aortic delivery system.

1. Rear Grip	7. RO Marker
2. Screw Gear	8. Spindle
3. Retractor Handle	9. Sleeve
4. Retractor Trigger	10. Tapered Tip
5. Front Grip	11. Sideport Extension
6. Graft Cover	12. Rear Luer

[figure not shown]
**Figure 2: Endurant Evo Aortic Delivery System**

The atraumatic polymeric aortic tapered tip is overmolded on the distal end of the nitinol guidewire tube to facilitate tracking through tortuous and calcified vessels. Attached to the proximal end of the tapered tip is a metallic sleeve that holds the suprarenal stent constrained on the spindle. The spindle is a polyether ether ketone (PEEK) overmold on the distal end of the spindle-tube to hold the proximal end of the suprarenal stent axially stationary before release. The aortic tapered tip, [REDACTED], and the distal end of the graft cover are radiopaque and aid in fluoroscopic visualization. Hemostasis is maintained by the seals within the delivery system that are designed to help minimize blood loss during the procedure. Retraction of the graft cover while the suprarenal stent is held by the spindle and sleeve allows for accurate positioning and deployment of the body of the stent graft components.

### *Iliac Delivery System*

The working length of the iliac delivery system is  $57 \pm 2\text{cm}$ . The Endurant Evo iliac delivery system (Figure 3) is constructed of four concentric single lumen shafts (an outer polymer graft cover with a hydrophilic coating, a polymer middle member shaft, [REDACTED], and a PEEK guidewire tube inner lumen).

[REDACTED] A polymeric, atraumatic tapered tip is overmolded at the distal end of the PEEK guidewire tube lumen to facilitate tracking through tortuous and calcified vessels. The tapered tip, [REDACTED], and the distal end of the graft cover are radiopaque and aid in fluoroscopic visualization. Hemostasis is maintained by seals within the delivery system that are designed to minimize blood loss during the procedure. The deployment of the self-expanding stent graft components is facilitated by the retraction of the graft cover.

1. Rear Grip	6. Graft Cover
2. Screw Gear	7. RO Tip
3. Retractor Handle	8. Tapered Tip
4. Retractor Trigger	9. Sideport Extension
5. Front Grip	10. Rear Luer

**Figure 3: Endurant Evo Iliac Delivery System**

The Endurant Evo AAA stent graft system is an investigational class III device in all geographies and is labeled with all the required statements per geography:

- Europe: "Exclusively for clinical investigations" (including translations into local languages)
- United States: "CAUTION: Investigational Device. Limited by Federal Law (USA) to Investigational Use"

The use of the Endurant Evo AAA stent graft system is limited to this clinical investigation and has to be done according to the clinical investigational plan and the Instructions for Use (IFU). Required Investigator training for the use of the Endurant Evo AAA stent graft system is described in Section E. 4.

### B.2.2 Indications for Use

The Endurant Evo bifurcated stent graft is indicated for the endovascular treatment of infrarenal abdominal aortic or aortoiliac aneurysms. The Endurant Evo aorto-uni-iliac (AUI) stent graft is indicated for the endovascular treatment of infrarenal abdominal aortic or aortoiliac aneurysms in subjects whose anatomy does not allow the use of a bifurcated stent graft. The Endurant Evo AAA stent graft system is indicated for use in subjects with the following characteristics:

- adequate iliac or femoral access that is compatible with vascular access techniques (femoral cutdown or percutaneous), devices, and accessories
- proximal neck length of
  - ≥10 mm and infrarenal neck angulation of ≤60° and suprarenal neck angulation of ≤45°, or
  - ≥15 mm and infrarenal neck angulation of ≤75° and suprarenal neck angulation of ≤60°
- aortic neck diameters with a range of 18 mm to 32 mm
- distal fixation lengths of ≥20 mm
- iliac diameters with a range of 7 mm to 25 mm
- morphology suitable for aneurysm repair

**Note:** Proximal neck length refers to minimum seal zone.

## C STUDY PLAN

### C.1 Study Objectives

The purpose of the Endurant Evo US Clinical Trial is to demonstrate that the Endurant Evo AAA stent graft system is safe and effective for endovascular treatment of infrarenal abdominal aortic or aortoiliac aneurysms. The clinical evidence collected as part of this trial will be used in conjunction with data collected during the concurrently enrolling Endurant Evo International Clinical Trial to support PMA Approval of the Endurant Evo AAA Stent graft system.

#### C.1.1 Primary Objectives

The primary safety objective is to demonstrate the safety of the Endurant Evo AAA Stent graft system for the endovascular treatment of abdominal aortic or aortoiliac aneurysms. Safety will be assessed through the proportion of subjects who have a Major Adverse Events (MAE) reported within 30-days post-implantation.

The primary effectiveness objective is to demonstrate successful delivery and deployment of the Endurant Evo AAA Stent graft system with successful removal of the delivery system during the index procedure as well as the treatment success at 12 months.

(See section *C.2.1 Primary Endpoints* for a detailed description of the evaluation criteria used to assess Primary Objectives)

#### C.1.2 Secondary Objectives

Secondary objectives include descriptive analyses of secondary endpoints as well as acute procedural and clinical utility measures.

(See section *C.2.2 Secondary Endpoints* for a detailed description of the evaluation criteria used to assess Secondary Objectives)

## C.2 Clinical Endpoints

### C.2.1 Primary Endpoints

#### C.2.1.1 Primary Safety Endpoint

The primary safety endpoint is defined as the proportion of subjects experiencing a MAE within 30 days post-implantation. MAEs include the occurrence of any of the following events:

- All-cause mortality
- Bowel ischemia
- Myocardial infarction
- Paraplegia
- Procedural blood loss  $\geq 1000$  cc
- Renal failure
- Respiratory failure
- Stroke

Detailed definitions of MAEs are provided in Appendix L.2.

#### C.2.1.2 Primary Effectiveness Endpoint

The primary effectiveness endpoint is defined as the proportion of subjects with both technical success at the time of index procedure and treatment success at 12 months post-implantation. Successful aneurysm treatment is achieved based on the following criteria:

- Technical success at the index procedure (as assessed intra-operatively) is defined as successful delivery and deployment of the Endurant Evo AAA Stent graft system in the planned location and with no unintentional coverage of both internal iliac arteries or any visceral aortic branches and with successful removal of the delivery system

AND

[figure not shown]
- Treatment success consisting of freedom from:
  - AAA diameter increase, defined as > 5 mm increase in maximum diameter as measured on CT scan (or MRA/MRI) at 12-month follow-up as compared to 1-month imaging
  - Types I and III endoleaks at 12-month follow-up including those requiring intervention through 12 months
  - Aneurysm rupture within 365 days
  - Conversion to surgery within 365 days
  - Stent graft migration resulting in a serious adverse event or requiring secondary intervention through 12 months
  - Stent graft occlusion through 12 months

### C.2.2 Secondary Endpoints

The following secondary endpoints will be evaluated:

- All cause-mortality within 30, 183, and 365 days
- Aneurysm-related mortality within 30, 183, and 365 days
- Secondary procedures to correct Type I and III endoleaks within 183 and 365 days
- Secondary procedures within 183 and 365 days
- Serious adverse events within 30, 183, and 365 days
- Conversion to open surgery within 183 and 365 days
- Aneurysm rupture within 183 and 365 days major adverse events within 183 and 365 days
- Stent graft migration at 6- and 12-month follow-up visits (as compared to 1-month imaging)
- Aneurysm expansion >5 mm at 6- and 12-month follow-up visits (as compared to 1-month imaging)
- All endoleaks based on imaging findings at 1-, 6-, and 12-month follow-up visits
- Stent graft occlusions based on imaging findings through 1-, 6- and 12 months
- Device deficiencies based on imaging findings through 6 and 12 months

Detailed definitions for secondary endpoints are provided in Appendix L.2.

### C.3 Study Hypothesis

The Endurant Evo US Clinical Trial will focus on balancing pre- and post-market clinical data to establish safety and effectiveness. Study success is defined as rejecting the null hypothesis for the primary safety endpoint test ( $\geq 20\%$ ), with a condition upon rejecting the null hypothesis for the post-market primary effectiveness test ( $\leq 80\%$ ). As such, the following analyses will be submitted:

- Pre-market: 30-day primary safety endpoint (hypothesis based, see H.1)
- Pre-market: 6-month effectiveness analysis (descriptive)
- Post-market: 12-month primary effectiveness endpoint (hypothesis based, see H.1)

The proposed clinical strategy described in this section will allow for appropriate evaluation of the safety and effectiveness of the Endurant Evo AAA stent graft system. Safety will be established through the hypothesis-based primary safety endpoint at 30 days. Reasonable assurance of effectiveness will be provided via the pre-market 6-month analysis and then confirmed at the 12-month post-market primary effectiveness endpoint.

### C.4 Study Population

The study population will include those subjects who are appropriate candidates for endovascular repair of infrarenal abdominal aortic or aortoiliac aneurysms, and who meet the Inclusion/Exclusion criteria (defined in Section D).

### C.5 Study Design

The Endurant Evo US Clinical Trial is prospective, multi-center, pre-market, non-randomized, single-arm trial. The trial is designed to assess the clinical safety and performance of the Endurant Evo AAA Stent graft system.

Globally, a total of 140 subjects will be concurrently enrolled in the United States and outside the United States to support the primary endpoint. Up to 50% of subject data used to support PMA approval may come from subjects enrolled at sites outside of the US under a separate CE Mark study protocol; the Endurant Evo International Clinical Trial protocol. The Endurant Evo International Clinical Trial protocol and Endurant Evo US Clinical Trial protocol will be identical with respect to the inclusion/exclusion criteria, and follow up data collection.

Given the UADEs that have occurred within the Endurant Evo study (transition stent fracture, partial suprarenal stent detachment, and suprarenal stent fracture), enrollment was terminated. Total global enrollment, upon termination, was 139 subjects. This includes 70 subjects enrolled in the United States and 69 enrolled outside the United States.

### C.6 Randomization and Blinding

The study is a single arm study, therefore neither randomization nor blinding are applicable to this clinical trial.

### C.7 Sample Size

The sample size for the Endurant Evo global program is calculated for both the primary safety endpoint and the primary effectiveness endpoint.

It is expected that the Endurant Evo AAA stent graft system will result in a MAE rate at 10% with respect to the primary safety endpoint and 90.5% treatment success for the primary effectiveness

 A minimum of 50 subjects will be enrolled with the high neck angulation indication (defined as proximal neck length  $\geq 15$  mm, infrarenal neck angulation  $> 60^\circ$  and  $\leq 75^\circ$  and suprarenal neck angulation  $\leq 60^\circ$ ). If a minimum of 50 subjects are not enrolled as part of the first 140 subject cohort, Medtronic will continue enrollment for the high angulation indication but submit the PMA application to obtain approval for the 60°angulation indication with the 140 subject cohort data. A minimum of 70 subjects enrolled in the study will have percutaneous access.

endpoint according to its predicates' performances shown in Table C-1.

**Table C-1: Clinical Data from Talent AAA eLPS and Endurant Studies**

Predicates	MAE within 30 Days	Successful Aneurysm Treatment at 12 Months
Talent AAA eLPS Arm	11% (18/166)	86% (107/125)
Endurant IDE Bifurcated Arm	4% (6/150)	95% (115/121)
Endurant IDE AUI Arm (P100021/S021)	11% (5/44)	97% (35/36)

In order to pass both hypothesis tests with an overall study power of 80%, a sample size of 119 evaluable subjects will be required to pass each hypothesis with 90% statistical power (target significance level is 0.025.) To account for attrition of 15% (85% imaging compliance) at 12 months, 140 subjects will be enrolled globally to ensure at least 119 evaluable subjects. Note that a minimum of 50 subjects will be enrolled with the high neck angulation indication and a minimum of 70 subjects will be enrolled with percutaneous access If a minimum of 50 high angle indication subjects are not enrolled as part of the first 140 subject cohort, Medtronic will continue enrollment for the high angulation indication but submit the PMA application to obtain approval for the 60° angulation indication with the 140 subject cohort data.

At a minimum, 50% of the total global subject cohort will be enrolled in the Endurant Evo US Clinical Trial. The other subjects will be enrolled in the Endurant Evo International Clinical Trial. This trial is designed for the data to be pooled with the Endurant Evo US Clinical Trial. More details about the poolability of Endurant Evo US Clinical Trial subjects and Endurant Evo International Clinical Trial subjects can be found in H.1.

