**Statistical Hypothesis:**

The primary safety endpoint will be tested against a predetermined safety Performance Goal (PG) using the following statistical hypotheses:

$$H_0: p \geq 20\% \text{ vs. } H_1: p < 20\%$$

where  $p$  is the proportion of subjects experiencing a MAE within 30 days of the index procedure in the target population of subjects treated with the Endurant Evo AAA Stent graft system and 20% is the safety PG.

The primary effectiveness endpoint will be tested against a predetermined effectiveness PG using following statistical hypotheses:

$$H_0: q \leq 80\% \text{ vs. } H_1: q > 80\%$$

where  $q$  is the proportion of subjects who have a successful aneurysm treatment in the target population of subjects treated with the Endurant Evo AAA Stent graft system and 80% is the effectiveness PG.

If the null hypothesis ( $H_0$ ) is rejected at the one-sided 0.025 statistical significance level, it is considered that the PG for the associated endpoint has been reached.

Both safety and effectiveness endpoints are dichotomous study outcomes; hence, an exact method based on the binomial distribution will be used for the hypothesis testing.

Subset analyses by-sex, by-race (based on subjects enrolled in the US only, since collection of race and ethnicity data may not be allowed outside the US as per local law and regulation), and by-region/study site will be performed on the primary safety and effectiveness endpoints using descriptive statistics and reviewed for clinical significant difference. Sensitivity analysis using tipping point method may be performed, as needed, to assess the impact of missing data.

No inferential statistical analysis is planned for secondary or additional study endpoints. Descriptive statistics will be provided for all endpoints as well as baseline variables.

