### 3.3. Sample Size Consideration

The sample size for the Endurant Evo global program is calculated for both the primary safety endpoint and the primary effectiveness endpoint.

It is expected that the Endurant Evo AAA stent graft system will result in a MAE rate at 10% with respect to the primary safety endpoint and 90.5% treatment success for the primary effectiveness endpoint according to its predicates' performances shown in Table 1.

In order to pass both hypothesis tests with an overall study power of 80%, a sample size of 119 evaluable subjects will be required to pass each hypothesis with 90% statistical power (target significance level is 0.025.) To account for attrition of 15% (85% imaging compliance) at 12 months, 140 subjects will be enrolled globally to ensure at least 119 evaluable subjects. Note that a minimum of 50 subjects will be enrolled with the high neck angulation indication and a minimum of 70 subjects will be enrolled with percutaneous access. If a minimum of 50 high angle indication subjects are not enrolled as part of the first 140 subject cohort, Medtronic will continue enrollment for the high angulation indication but submit the PMA application to obtain approval for the 60° angulation indication with the 140 subject cohort data.

Table 1: Clinical Data from Talent AAA eLPS and Endurant Studies

Predicates	MAE within 30 Days	Successful Aneurysm Treatment at 12 Months
Talent AAA eLPS Arm	11% (18/166)	86% (107/125)
Endurant IDE Bifurcated Arm	4% (6/150)	95% (115/121)
Endurant IDE AUI Arm	11% (5/44)	97% (35/36)

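### The 85% imaging compliance behind the 119 evaluable subjects has no source and lies above all three predicate ratios in Table C-1; about 109–112 evaluable and overall power of about 76–77% are better supported

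*Protocol*

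**What the plan says.** Protocol C.7 expects that the device "will result in a MAE rate at 10% with respect to the primary safety endpoint and 90.5% treatment success for the primary effectiveness" endpoint, and names the predicates in Table C-1 as the basis. The text under the table derives the sample size: "overall study power of 80%, a sample size of 119 evaluable subjects will be required to pass each hypothesis with 90% statistical power". It then inflates for missing 12-month outcomes: "To account for attrition of 15% (85% imaging compliance) at 12 months, 140 subjects will be enrolled globally", and presents this as securing at least 119 evaluable subjects. SAP 3.3 repeats the premise: "To account for attrition of 15% (85% imaging compliance) at 12 months". Neither document says where the 85% comes from.

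Protocol H.1 and SAP 8.3 rule out imputation of outcomes, apart from incomplete onset dates, and leave the tipping-point analysis optional. SAP 8.4 bases the imaging components of the effectiveness endpoint on core-lab reads, with readable images in the denominators of Table 4. Protocol C.5 records that enrolment closed at 139.

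**The concern.** The section relies on the predicates for the event rates but not for the share of subjects who had a 12-month outcome, although both stand in Table C-1. Every arm has a markedly smaller denominator at 12 months than at 30 days, and no arm's ratio reaches 85%.

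Because outcomes are not imputed, each missing 12-month result reduces the number on which effectiveness is tested. Rejecting the effectiveness null is a condition of study success (C.3). If the evaluable number is overstated, a missed effectiveness goal would be read against a power that the design did not have. The 30-day safety test is essentially unaffected: SAP Table 3 counts any subject without an MAE who has at least one day in the study.

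**Working it through.** **Inputs.** Each null is tested as "rejected at the one-sided 0.025 statistical significance level", and "an exact method based on the binomial distribution will be used for the hypothesis testing" (Protocol H.1). For safety, "20% is the safety PG" and the assumed MAE rate is 10%. For effectiveness, "80% is the effectiveness PG" and the assumed success rate is 90.5%. Enrolled: 140 planned, 139 actual.

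**1. The plan's own figures.** The effectiveness rule is the smallest c with P(X ≥ c | n, 0.80) ≤ 0.025; power is P(X ≥ c | n, 0.905).
- n = 119: c = 104, actual alpha 0.0241, power 90.1%.
- 119 / 0.85 = 140.
- Safety at n = 140: at most 18 MAEs, power 89.4%.
- Overall, if independent: 0.901 × 0.894 = 80.6%.

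The stated figures reproduce when safety uses all enrolled subjects. The open question is the 85%.

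**2. Ratios in Table C-1** (12-month / 30-day denominator, exact 95% interval).
- Talent: 125/166 = 75.3% (68.0–81.7%)
- Endurant bifurcated: 121/150 = 80.7% (73.4–86.7%)
- Endurant AUI: 36/44 = 81.8% (67.3–91.8%)
- Endurant arms together: 157/194 = 80.9% (74.7–86.2%)
- All arms: 282/360 = 78.3% (73.7–82.5%)

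**3. Why single values of n mislead.** Exact power is saw-toothed: 84.8% at n = 109, 88.4% at n = 113, 84.9% at n = 118, 90.1% at n = 119. Losing one subject from 119 costs as much as losing ten. The evaluable number N is therefore treated as random, N ~ Binomial(139, r), and power is averaged: Σ P(N = n) × power(n).

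**4. Results.** Safety at n = 139 (at most 18 MAEs) has power 90.0%. Overall power is the product, assuming independence.

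| Evaluable fraction r | 139 × r | Effectiveness power | Overall power | P(N ≥ 119) |
|---|---|---|---|---|
| 85% (plan) | 118.15 | 87.5% | 78.7% | 48% |
| 81.8% (AUI) | 113.73 | 85.9% | 77.3% | 15% |
| 80.9% (Endurant together) | 112.49 | 85.4% | 76.8% | 9% |
| 80.7% (bifurcated) | 112.13 | 85.3% | 76.7% | 8% |
| 78.3% (all arms) | 108.88 | 83.9% | 75.5% | 2% |
| 75.3% (Talent) | 104.67 | 82.1% | 73.9% | 0.2% |

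**5. Share due to compliance.** Against the plan's 85% on the same averaged basis, overall power falls by 78.7 − 76.8 = 1.9 points (Endurant arms) or 78.7 − 75.5 = 3.2 points (all arms). The rest of the distance to 80% comes from treating N as random, and is present at 85% too.

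**The case against.** The arithmetic in C.7 is sound, and 85% is a planning assumption. The strongest points in its defence are these.

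- **The denominators are unlabelled.** Table C-1 does not say that the 30-day counts are the subjects due at 12 months, or why the 12-month counts are smaller. The table's footnote cites regulatory submissions whose data cut and evaluability rules are not shown, so incomplete follow-up at the cut cannot be excluded. This stands as a caveat. It could also work the other way: if the 30-day counts omit treated subjects, the true fractions are lower.
- **The closest predicates do not exclude 85%.** The device belongs to the Endurant platform, and the interval for the Endurant arms together includes 85%. Only the Talent arm and the pooled figure that it pulls down exclude it. This also stands. The Endurant arms do not refute 85%, but their point estimate does not support it either.
- **The predicate fractions may not transfer.** This trial has a wide 12-month analysis window (days 305–548), counts subjects with an event in the Table 4 denominators through 12 months even without a 12-month image, and has extra surveillance imaging recommended by the DMC. Compliance could be better here. The plan does not make that argument, and these features could serve as the missing justification.
- **Enrolment is closed.** True, so a larger trial is not a remedy. C.7 and SAP 3.3 nevertheless still state 85%, 119 and 80% as current text, and SAP section 1 makes the SAP's analyses the basis of the study report.

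A reader might infer that the plan's own data contradict the 85%, or that low compliance alone takes power from 80% to 76%. The documents support neither. The first ignores the unlabelled denominators and the Endurant interval. The second sets a fixed n of 119 against a random one.

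**Conclusion.** The point holds at a moderate size. The 85% is unsourced and above every predicate ratio in the table on which the section relies. With 139 enrolled, about 109–112 evaluable subjects should be expected (range 105–114). At least 119 is not assured: the chance is 2–9% at the all-arm and Endurant fractions, and only 48% at 85%.

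Averaged effectiveness power is about 84–85% (range 82–86%) and overall power about 76–77% (range 74–77%), against the stated 90% and 80%. Compliance accounts for about 2–3 points of the overall shortfall.

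These figures assume that the 30-day denominators are the subjects at risk, that the predicate fractions carry over, that the true rates are the planned 10% and 90.5%, and that the two tests are independent. Without independence, overall power at the all-arm fraction is bounded only by 0.839 + 0.900 − 1 = 73.9% below and 83.9% above.

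**What to change.** In Protocol C.7 and SAP 3.3:

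1. Give a source or reason for 85% compliance, or replace the 15% attrition with the predicate range of 18–25%.
2. Delete the clause that presents 140 enrolled as securing at least 119 evaluable subjects.
3. Restate effectiveness power as about 84–85% (range 82–86%) and overall power as about 76–77% (range 74–77%), and state the denominator and independence assumptions.
4. Commit to reporting the attained evaluable number, with the exact power at that number under the planned 90.5%.

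This takes a few sentences in each document. It adds no subjects and changes no test or threshold. The only downside is a less favourable stated power.
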